Theta Burst Stimulation for Schizophrenia

NCT03288779

Document Date: May 4, 2018

Theta Burst Stimulation in Schizophrenia

1. Protocol Title – Theta Burst Stimulation in Schizophrenia

2. Purpose of the study

Aim1: Evaluate the effect of theta burst stimulation (TBS) on working memory (WM) in patients with schizophrenia. Hypothesis 1 – There will be significant improvement in WM compared to baseline with one session of TBS.

Aim 2: Evaluate the effect of TBS on gamma and theta oscillations as measured from EEG. Hypothesis 2 – Increase in theta oscillation spectral power and decrease in spectral power of gamma oscillations with one session of TBS.

3. Background and Significance

Schizophrenia is an illness known to have cognitive deficits, with a chronic and variable course. There is extensive research on cognitive deficits, with working memory, processing speed and verbal memory being some of the domains affected(1, 2). Some modalities of treatment that have been tried to reverse these cognitive deficits are medications and cognitive behavioral therapy with minimal benefits (3). A few studies have shown modulation of working memory with routine repetitive transcranial magnetic stimulation at frequencies not exceeding 10 to 20 Hz of stimulation (4, 5). Other studies have shown the working memory to be related to gamma oscillations. A few studies have also shown that transcranial magnetic stimulation (TMS) modulates these gamma oscillations as well. There is an extensive body of literature that shows that working memory has contributions from theta and gamma oscillations in the brain. **Theta burst stimulation (TBS) is a form of transcranial magnetic stimulation (TMS)**, that entrains gamma and theta frequencies in the brain. It could be the most appropriate form of brain stimulation for improving cognition in schizophrenia patients because it has been shown to modulate brain oscillations in small samples of patients (6-9). The area for targeting would be the dorsolateral prefrontal cortex which is the site of origin of the gamma oscillations and plays a significant role in working memory (10, 11).

4. Design and Procedures

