4.1 Study protocol overview

The study is designed to be a pilot one evaluating the effect of TBS on WM in patients with schizophrenia. We plan to screen 20 subjects to have 10 participants.

The participant is not responsible for any research-related costs. The participants will be under the purview of their physician who is responsible for the participant's care. The clinical team will first contact potential participants before contact by study team. If subject would like to participate, then the study team will approach subject for the study. The study team will ask for participants' permission to contact their primary care team on the psychiatry inpatient floor so that information can be provided to the primary care team regarding the participant's enrollment during the study.

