4.2 Screening

We plan to recruit both inpatients and outpatients.

To recruit inpatients, potential participants will be discussed with the primary care team caring for the patient on Williams' Unit which is the inpatient psychiatry floor at Duke Medical Center. Once a potential participant has been identified, the clinical team will first contact potential participant before contact by study team. If

Theta Burst Stimulation in Schizophrenia

subject would like to participate, a study team person will approach the patient, discuss the study and desire for participation in person with that individual on the inpatient unit. This will be done day 1. If agreeable the individual will be approached for consent on day 2. For consent, the study would be discussed with the patient by study personnel, and a member of the study team will administer the University of California, San Diego Brief Assessment of Capacity to Consent (UBACC) to ascertain validity of the consent given for the study. After providing informed consent participants will undergo a clinical assessment to confirm the inclusion/exclusion criteria.

Outpatients who contact the study team (after seeing the study on clinicaltrials.gov) will be screened over phone based on inclusion and exclusion criteria. If they fulfill criteria, they will be scheduled for the experiment. We do not plan to actively recruit outpatients using study flyers or other materials.

All female subjects in the reproductive age group will be tested for pregnancy using a commercially available test kit specified by Department of Obstetrics and Gynecology. The Pregnancy test must be negative to continue in the study. If sexually active, subjects must agree to use appropriate contraceptive measures for the duration of the study for inclusion. Medically acceptable contraceptives include: (1) surgical sterilization (such as a tubal ligation or hysterectomy), (2) approved hormonal contraceptives (such as birth control pills, patches, implants or injections), (3) barrier methods (such as a condom or diaphragm) used with a spermicide, or (4) an intrauterine device (IUD). Contraceptive measures such as Plan B (TM), sold for emergency use after unprotected sex, are not acceptable methods for routine use and will result in exclusion from the study.

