4.3 Transcranial Magnetic Stimulation (TMS) administration

On day 2, the patient would be transported from the inpatient unit to the TMS lab in the red zone on the fifth floor following screening and consent process. They would be accompanied by nursing staff. During their visit to the TMS lab a sample TMS session including motor threshold determination will be conducted.

Treatment Sessions

On day 2, subjects would also be administered left sided theta burst stimulation (TBS) with concomitant EEG monitoring. The subject will be seated in a chair. A 64-channel electrode cap may be applied to the head for EEG recording. EMG electrodes will be applied to the right hand for motor evoked potential (MEP) recording. Subjects will perform BACS before and after the TMS session. EEG and EMG will be recorded throughout the treatment sessions. For theta burst stimulation the active motor threshold would be 80 % as used in most theta burst studies detailed in this review. Subjects would receive theta burst stimulation comprising 50 Hz bursts given at 3 to 5 Hz for close to 10 minutes which comprises 60 trains and 1800 pulses. The subject will be monitored until MEPs return to baseline. A side effects checklist will be completed at the beginning and at the end of the experimental session. All sessions will be performed by one of the protocol investigators, or by a trained and accredited research assistant supervised by the protocol investigators.

Methods:

Motor Threshold Determination:

Motor threshold (MT) is defined as the TMS pulse amplitude needed to elicit an EMG response of 50 μ V peak-to-peak average amplitude in a target muscle. MT is the standard in the field for determining the intensity of TMS for everyone to reduce seizure risk. The MEP for the right first dorsal interosseus (FDI) will be measured with EMG. The scalp region producing the largest amplitude MEP will be identified. At that scalp location, we will determine the TMS intensity eliciting average MEP amplitude of 50 μ V peak-to-peak in the first DI muscle

Theta Burst Stimulation in Schizophrenia

using an amplitude titration procedure (at least 5/10 trials). Individual MT will be used to determine the intensity of theta burst stimulation for everyone, as recommended by safety guidelines.

Application of theta burst stimulation (TBS)

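### All patients receive active TBS with no comparator, so the planned pre-post t test cannot attribute a working-memory change to TBS; separately, conflicting visit days leave the BACS retest interval unclear.

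*Combined protocol and SAP*

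**What the plan says.** Aim 1 in Section 2 is to "Evaluate the effect of theta burst stimulation (TBS) on working memory (WM) in patients with schizophrenia". Section 4.1 keeps that framing while calling the study a pilot: "The study is designed to be a pilot one evaluating the effect of TBS on WM in patients with schizophrenia". Section 11 plans several t tests to find out whether a single session can alter working memory and EEG, and limits recruitment to 10 because this is a pilot. Hypothesis 1 names the contrast: "There will be significant improvement in WM compared to baseline with one session of TBS".

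Section 4.3 gives the same active treatment to everyone: "On day 2, subjects would also be administered left sided theta burst stimulation (TBS) with concomitant EEG monitoring". It also says: "Subjects will perform BACS before and after the TMS session". No section describes a sham condition, control arm, crossover or practice adjustment. The healthy control sample in Section 4.5 serves only to norm the BACS scores. Digit Sequencing is the only task that Section 4.5 labels as working memory. Alternate forms are mentioned there for List Learning and Tower of London, but not for Digit Sequencing.

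On timing, Section 4.2 says of inpatients: "If agreeable the individual will be approached for consent on day 2", and then: "After providing informed consent participants will undergo a clinical assessment to confirm the inclusion/exclusion criteria". Of outpatients who pass the phone screen it says: "If they fulfill criteria, they will be scheduled for the experiment". Section 4.3 puts motor threshold determination at the Day 2 laboratory visit. The Section 4.7 table marks consent and the first BACS under Day 1, motor threshold under Day 1, and the second BACS under Day 2.

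**The concern.** The question asked is causal: does TBS change working memory? The quantity tested is the mean change in one treated group. That change is the sum of any TBS effect and everything else that differs between the two tests: familiarity with the task, expectancy, fatigue after a session, and day-to-day variation. These can push the score up or down.

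Followed as written, the plan could credit TBS with an improvement it did not cause, or miss a real effect masked by fatigue. The interval between the two tests bears on how large some of these influences are, and the schedule does not state that interval consistently.

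**Working it through.** **1. What can be reproduced.** The plan gives no effect size, SD, significance level or power for its sample of 10, so there is no stated calculation to reproduce. Section 11 does not say whether the t tests are paired or what level they use.

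**2. Illustration of the attribution problem.** Taken from the documents: n = 10. Assumed: paired t test, two-sided 5% level, a net non-TBS shift expressed in baseline SDs, equal SDs before and after, and a retest correlation r. The documents give neither the shift nor r for Digit Sequencing. The only reliability figure, an ICC above .80 in Section 4.5, is for the BACS composite and has no retest interval.

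- SD of change = √(2(1 − r)) baseline SD
- Noncentrality = (net shift / SD of change) × √10
- df = 9, critical t = 2.262
- Chance of a significant improvement = upper tail of the noncentral t beyond 2.262

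Example with r = 0.8 and shift +0.5: SD of change = √0.4 = 0.632; noncentrality = 0.5/0.632 × 3.162 = 2.50; upper tail = 0.606.

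Chance of a significant improvement when the TBS effect is zero:

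| r | SD of change | +0.1 SD | +0.2 SD | +0.3 SD | +0.5 SD |
|---|---|---|---|---|---|
| 0.5 | 1.00 | 0.047 | 0.082 | 0.134 | 0.293 |
| 0.8 | 0.63 | 0.065 | 0.144 | 0.269 | 0.606 |
| 0.9 | 0.45 | 0.093 | 0.244 | 0.474 | 0.881 |

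With no shift the figure is 0.025 for any r.

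A downward shift works the other way. With a true TBS gain of 0.5 SD and a shift of −0.2 SD, the net change is 0.3 SD. The chance of a significant improvement falls from 0.293 to 0.134 at r = 0.5, and from 0.606 to 0.269 at r = 0.8.

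**3. Precision of the recommended estimate.** The 95% confidence interval half-width is 2.262 × SD of change / √10, that is 0.72, 0.45 or 0.32 baseline SD at r = 0.5, 0.8 or 0.9.

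**4. Schedule, side by side.**

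| Item | Text of 4.2 and 4.3 | Table in 4.7 |
|---|---|---|
| Consent | Day 2 (4.2, inpatients) | Day 1 |
| Motor threshold | Day 2 (4.3) | Day 1 |
| BACS before TBS | Undated, in the Day 2 description (4.3) | Day 1 |
| TBS | Day 2 (4.3) | Day 2 |
| BACS after TBS | After the session (4.3) | Day 2 |

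Read alone, 4.2 and 4.3 can describe a single study day with a same-day retest. The 4.7 table describes two days, with a retest about one day later. If the consent day of 4.2 is combined with the BACS day of 4.7, the first BACS falls before consent.

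**The case against.** The strongest reply is that this is a declared 10-patient pilot. Hypothesis 1 openly states a comparison with baseline, Section 11 asks only whether TBS can have an effect, and no section commits to claiming efficacy after a significant result. Rejecting zero change when a real retest shift exists is not an error for that contrast; it misleads only under a causal reading. This stands in part. A single-group pilot is legitimate, and Hypothesis 1 is not the sentence at fault. But Aim 1, Section 4.1 and Section 11 do pose the causal question, and pilot status explains the sample size without supplying attribution.

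It can also be said that the illustration depends wholly on assumed shifts and correlations and that confounded change is generic to uncontrolled pilots. That is correct. The figures show how the test behaves; they are not evidence of bias in this trial.

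On the schedule, a reader might infer that the analysis baseline is not fixed, or that testing before consent is planned. The documents do not support either. Each source describes only one pre-TBS BACS, and the undated test in 4.3 is compatible with the Day 1 mark in 4.7. Motor threshold timing does not move the BACS. Testing before consent arises only by combining the consent day of one section with the BACS day of another. Nor is the silence of 4.2 on the outpatient BACS day a gap in itself, because the 4.7 table is not limited to inpatients.

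**Conclusion.** The attribution point holds. The planned test can show that working-memory scores changed; it cannot show that TBS changed them. This follows from the design as described and does not depend on the illustrative figures. The size and direction of any non-TBS shift are unknown, so no particular false-positive rate should be read from the table. The documents also give no ground for concluding that the pilot is invalid or must add a sham arm; the mismatch is between the wording and the design.

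Separately, the contradictions over the days of consent and motor threshold are real. What they leave open, together with the undated first BACS in 4.3, is the retest interval (same day or about one day) and the order of consent and first BACS if the consent day in 4.2 governs.

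**What to change.** 1. Reword Aim 1, Section 4.1 and Section 11 so that the objective is to estimate the post-minus-baseline change in working memory. Name Digit Sequencing as the Aim 1 measure if that is intended. Report the mean change with a two-sided 95% confidence interval, and state that the change is not attributed to TBS because there is no comparison group.
2. Reconcile Sections 4.2, 4.3 and 4.7 on the days of consent and motor threshold. State one time for the baseline BACS, after consent, that applies to all patients, inpatients and outpatients alike.

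Both items are text amendments and need no extra patients, tests or visits. The price of the first is a weaker claim. Under the second, some testing may move between days, depending on how the schedule is reconciled.

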4.1 Study protocol overview

The study is designed to be a pilot one evaluating the effect of TBS on WM in patients with schizophrenia. We plan to screen 20 subjects to have 10 participants.

The participant is not responsible for any research-related costs. The participants will be under the purview of their physician who is responsible for the participant's care. The clinical team will first contact potential participants before contact by study team. If subject would like to participate, then the study team will approach subject for the study. The study team will ask for participants' permission to contact their primary care team on the psychiatry inpatient floor so that information can be provided to the primary care team regarding the participant's enrollment during the study.

4.2 Screening

We plan to recruit both inpatients and outpatients.

To recruit inpatients, potential participants will be discussed with the primary care team caring for the patient on Williams' Unit which is the inpatient psychiatry floor at Duke Medical Center. Once a potential participant has been identified, the clinical team will first contact potential participant before contact by study team. If

Theta Burst Stimulation in Schizophrenia

subject would like to participate, a study team person will approach the patient, discuss the study and desire for participation in person with that individual on the inpatient unit. This will be done day 1. If agreeable the individual will be approached for consent on day 2. For consent, the study would be discussed with the patient by study personnel, and a member of the study team will administer the University of California, San Diego Brief Assessment of Capacity to Consent (UBACC) to ascertain validity of the consent given for the study. After providing informed consent participants will undergo a clinical assessment to confirm the inclusion/exclusion criteria.

Outpatients who contact the study team (after seeing the study on clinicaltrials.gov) will be screened over phone based on inclusion and exclusion criteria. If they fulfill criteria, they will be scheduled for the experiment. We do not plan to actively recruit outpatients using study flyers or other materials.

All female subjects in the reproductive age group will be tested for pregnancy using a commercially available test kit specified by Department of Obstetrics and Gynecology. The Pregnancy test must be negative to continue in the study. If sexually active, subjects must agree to use appropriate contraceptive measures for the duration of the study for inclusion. Medically acceptable contraceptives include: (1) surgical sterilization (such as a tubal ligation or hysterectomy), (2) approved hormonal contraceptives (such as birth control pills, patches, implants or injections), (3) barrier methods (such as a condom or diaphragm) used with a spermicide, or (4) an intrauterine device (IUD). Contraceptive measures such as Plan B (TM), sold for emergency use after unprotected sex, are not acceptable methods for routine use and will result in exclusion from the study.

4.3 Transcranial Magnetic Stimulation (TMS) administration

On day 2, the patient would be transported from the inpatient unit to the TMS lab in the red zone on the fifth floor following screening and consent process. They would be accompanied by nursing staff. During their visit to the TMS lab a sample TMS session including motor threshold determination will be conducted.

Treatment Sessions

On day 2, subjects would also be administered left sided theta burst stimulation (TBS) with concomitant EEG monitoring. The subject will be seated in a chair. A 64-channel electrode cap may be applied to the head for EEG recording. EMG electrodes will be applied to the right hand for motor evoked potential (MEP) recording. Subjects will perform BACS before and after the TMS session. EEG and EMG will be recorded throughout the treatment sessions. For theta burst stimulation the active motor threshold would be 80 % as used in most theta burst studies detailed in this review. Subjects would receive theta burst stimulation comprising 50 Hz bursts given at 3 to 5 Hz for close to 10 minutes which comprises 60 trains and 1800 pulses. The subject will be monitored until MEPs return to baseline. A side effects checklist will be completed at the beginning and at the end of the experimental session. All sessions will be performed by one of the protocol investigators, or by a trained and accredited research assistant supervised by the protocol investigators.

Methods:

Motor Threshold Determination:

Motor threshold (MT) is defined as the TMS pulse amplitude needed to elicit an EMG response of 50 μ V peak-to-peak average amplitude in a target muscle. MT is the standard in the field for determining the intensity of TMS for everyone to reduce seizure risk. The MEP for the right first dorsal interosseus (FDI) will be measured with EMG. The scalp region producing the largest amplitude MEP will be identified. At that scalp location, we will determine the TMS intensity eliciting average MEP amplitude of 50 μ V peak-to-peak in the first DI muscle

Theta Burst Stimulation in Schizophrenia

using an amplitude titration procedure (at least 5/10 trials). Individual MT will be used to determine the intensity of theta burst stimulation for everyone, as recommended by safety guidelines.

Application of theta burst stimulation (TBS)

A magnetic coil will be placed on the scalp and held in place with frameless stereotaxic equipment, using a sophisticated method of coil placement that will coregister scalp positions directly onto an average brain template. This Frameless Stereotaxic System Brainsight offers real-time three-dimensional display of cortical localization as the TMS coil is moved across the scalp. This will be used for coil positioning. This system uses a programmed robot arm to precisely position the TMS coil, and maintain its position, within 1 mm of the brain target chosen. Earplugs will be worn to protect hearing and low-volume white noise will be played through TMS-compatible headphones to mask the sound of the coil clicks. The intensity of the theta burst stimulation will be 80% AMT as reported in a recent review on parameters of theta burst stimulation and a review on safety of the theta burst stimulation. The participant will be seated comfortably with headphones and earplugs to protect the subject's hearing. The theta burst stimulation parameters (comprising 50 Hz bursts given at 3 to 5 Hz for close to 10 minutes which comprises 60 trains and 1800 pulses) will be kept strictly within consensus safety limits: when kept within these limits, is deemed low risk (12).

4.5 Clinical and cognitive assessments/tasks

PANSS

The Positive and negative symptoms scale is used to assess the severity of schizophrenia. It has three subscales – positive, negative and general psychopathology. Each of these subscales had 7 items, the maximum scores on each of these subscales in 49, minimum score being 7.

BACS – Tasks to be done from the actual BACS battery of tests (13)

List Learning (Verbal Memory). Patients are presented with 15 words and then asked to recall as many as possible. This procedure is repeated 5 times. There are two alternate forms.

Digit Sequencing Task (verbal working Memory). Patients are presented with clusters of numbers of increasing length. They are asked to tell the experimenter the numbers in order, from lowest to highest.

Token Motor Task (Motor Speed). Patients are given 100 plastic tokens and asked to place them into a container as quickly as possible for 60 seconds.

Verbal Fluency. Tests of Category Instances (Semantic Fluency) and Controlled Oral Word Association Test (Letter Fluency) are administered. Patients are given 60 seconds to name as many words as possible within a given semantic category, and in two separate trials, patients are given 60 seconds to generate as many words as possible that begin with a given letter. The total number of words from the three trials is the outcome measure.

Tower of London (Reasoning and Problem Solving). Patients look at two pictures simultaneously. Each picture shows 3 different-colored balls arranged on 3 pegs, with the balls in a unique arrangement in each picture. The patients are told about the rules in the task and are asked to provide the least number of times the balls in one picture would have to be moved to make the arrangement of balls identical to that of the other, opposing picture. There are two alternate forms.

Symbol Coding (Attention and Processing Speed). As quickly as possible, patients write numerals 1–9 as matches to symbols on a response sheet for 90 seconds.

Each of the six measures are compared to a healthy control sample to create z-scores, and a composite score is calculated by summing these z-scores and calculating a z-score of that sum. (Keefe et al., 2004b). The composite score has high test-retest reliability in patients with schizophrenia and healthy controls (ICCs > .80).

Theta Burst Stimulation in Schizophrenia

